Therefore, this project is intended to compare the impact of different types of mouthguard on the speech performance of the athletes.

3. Research Questions

Is there any difference in speech performance when using 'boil and bite' and custom-fitted mouthguards?

4. Hypothesis

There is no difference in speech performance when using 'boil and bite' and custom-fitted mouthguards.

5. Aim and Objectives

Aim:

To compare the speech performance when using ‘boil and bite’ and custom-fitted mouthguards.

Objectives:

- a) To provide ‘boil and bite’ and custom-fitted mouthguards to athletes.
- b) To compare the immediate speech performance when using ‘boil and bite’ and custom-fitted mouthguards based on the auditive analysis and sonography of the mouthguard users.

6. Methodology

Selection criteria

The inclusion criteria are as follows:

- (i) adult female aged 18 years old and older;
- (ii) currently representing the nation and participating actively in rugby; and
- (iii) native speakers of Malay (national language).

The exclusion criteria are as follows:

- (i) did not play rugby within the last six months;
- (ii) edentulism;
- (iii) has used a mouthguard, orthodontic appliance or removable prosthodontics appliance within the last six months;
- (iv) known history of allergy to polymers; and
- (v) medical problems (ASA classification 3 and above).

Sample size

The sample size required is determined using G*Power software (available at: <http://www.gpower.hhu.de/>). The assumptions were an effect size of 0.25, 5% margin error, 80% power, within-subject measurements for the two types of mouthguard and control – not wearing any mouthguard. Correlation among measures was set at 0.5. This yielded a minimal sample size of 28. A drop-out rate of 10% was expected between first visit and fitting visit. Thus, the total sample size was adjusted to 32.

Interventions

Informed consent will be obtained before the commencement of the study. Interested participants must provide consent in written form. Simple questions will be asked to inquire about demographic details and the use of mouthguards and problems faced if not wearing one at the moment. Also, questions will be asked regarding existing speech impairment or disturbance.

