Dental examination will be carried out to all the consented participants to identify edentulism and prosthesis in the mouth. Dental impression will be taken using alginate impression material and rigid perforated stainless steel trays. The impressions will be rinsed under running tap water before spraying with disinfectant. The impressions will be transported in sealed and labelled zip-lock bags.

The impressions will be casted within the same day using Type II dental stone. Fabrication of mouthguards will be carried out by technicians using Essix mouthguard sheets and vacuum machine, with the edges extend towards the vestibule and even thickness of 4mm. Sharp edges will be smoothened.

At the fitting session, each participant will be given a ‘boil and bite’ mouthguard and a custom-fitted mouthguard. For ‘boil and bite’ mouthguards, the participants will immerse the

acrylic sheet in a bowl of hot water and fit the softened sheet on their dental arches, following the manufacturer's instructions. The completed custom mouthguards will be fitted. Any complaint of sharp edges will be handled. The players will then be instructed on the care of the mouthguards.

Immediately after fitting, speech performance will be recorded digitally in standardized conditions in a soundproof room. The volunteers will be asked to pronounce 5 two-syllable words with different consonant: *paku, bola, dadu, tatu*. Four recordings will be done, for each of the following conditions: (i) not using mouthguard; (ii) using a 'boil and bite' mouthguard; and (iii) using a custom-fitted mouthguard. The recording samples will be digitized into a computer.

Data analysis

Demographic data will be summarized using descriptive statistics. Audio recordings will be digitized with Praat software. Mean voice onset time will be compared using repeated measure ANOVA with post hoc Tukey test. However, if normality assumption is violated, the non-parametric equivalent, Friedman's test and post hoc Wilcoxon signed-rank test will be used.

7. References:

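### The one hypothesised comparison is tested at about 0.019 under Tukey but at 0.05 under an unadjusted Wilcoxon fallback, and an undefined normality judgement chooses between them

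*Combined protocol and SAP*

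**What the plan says.** The inferential plan is the short Data analysis paragraph in section 6. Mean voice onset time is compared by "repeated measure ANOVA with post hoc Tukey test". The alternative applies "if normality assumption is violated": Friedman's test is used instead, and "post hoc Wilcoxon signed-rank test will be used".

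The paragraph does not say:
- how normality is judged, on which quantity (raw values, residuals or paired differences), or at what cut-off;
- whether the Wilcoxon tests are run only after a significant Friedman test;
- whether their p-values are adjusted. An adjustment is neither named nor ruled out.

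The research question (section 3), the hypothesis (section 4), and the aim and objective (b) (section 5) all concern one pair: boil-and-bite versus custom-fitted. The no-mouthguard condition enters as a control in the sample size and recording paragraphs of section 6. No other section fills these gaps.

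**The concern.** Tukey's procedure spreads 5% over all three pairs. A Wilcoxon test with no adjustment spends the full 5% on each. The same difference between the two devices could therefore fail in one branch and pass in the other because the multiplicity rule changed, and not because one test suited the data better. The choice of branch is made after the data are seen, by a rule that is not written down. At stake is whether the trial's one question has a single threshold fixed in advance.

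**Working it through.** **Inputs from section 6, Sample size.** "The assumptions were an effect size of 0.25, 5% margin error, 80% power"; "within-subject measurements for the two types of mouthguard and control", which gives m = 3 conditions and 3 pairs; "Correlation among measures was set at 0.5"; "This yielded a minimal sample size of 28"; 10% drop-out, giving 32.

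**Assumptions.** The effect size is Cohen's f, sphericity holds, and pairwise tests are two-sided.

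**1. The plan's own figure.** λ = f²·n·m/(1 − ρ), with 2 and 2(n − 1) degrees of freedom.
- n = 28: λ = 0.0625 × 28 × 3 / 0.5 = 10.5; power 81.2%.
- n = 27: λ = 10.125; power 79.6%.
- So 28 is reproduced. 28/0.9 = 31.1, rounded up to 32, is reproduced too.

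**2. Level per pair.**
- Tukey, n = 28: q(0.05; 3, 54) = 3.408; 3.408/√2 = 2.410; two-sided p on 54 df = 0.0194. At n = 32 it is again about 0.0194.
- Wilcoxon with no adjustment: 0.05, which is 0.05/0.0194 = 2.6 times as large.

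**3. Familywise error, all three conditions equal.** Simulation with 40,000 trials per scenario, n = 28 and 32, correlation 0.5, normal and lognormal data:

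| Rule | At least one false positive |
|---|---|
| Tukey | 4.1–5.1% |
| Wilcoxon, no adjustment, only after Friedman p ≤ 0.05 | 4.0–4.2% |
| Wilcoxon, no adjustment, no gate | 12.1–12.7% |

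Three independent tests would give 1 − 0.95³ = 14.3%.

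**4. The hypothesised pair, devices equal but both different from none.** False positives for that pair are 1.6–2.0% under Tukey and 4.8–4.9% under unadjusted Wilcoxon, with or without the Friedman gate. The large effect against no mouthguard opens the gate, so it does not restrain this pair.

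**5. How often the switch fires.** The plan gives no rule. Assume Shapiro-Wilk at 5% on each condition (4,000 trials per scenario). It fires in about 15% of normal trials and about 100% of lognormal trials. With all conditions equal, the whole procedure has this familywise error:
- normal data: 5.7–6.3% ungated, 4.7–5.0% gated;
- lognormal data: 12.3–12.8% ungated, 3.9–4.1% gated.

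**6. Effect on conclusions.** Assume normal data, n = 28, and means of 0 (none), 0.8 and 0.4 SD (the two devices). The paired difference has SD √(2 × (1 − 0.5)) = 1, so the noncentrality is 0.4 × √28 = 2.117.
- Tukey, critical value 2.410 on 54 df: power about 39%.
- Paired t test at 5%, critical value 2.052 on 27 df: power about 53%.
- In simulation (10,000 trials), unadjusted Wilcoxon finds the pair significant in 51% of trials ungated and 49% gated. In 11–12% of trials the same data pass only in the Wilcoxon branch.

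**7. Error control of the fix.** If all conditions are equal, any false positive requires the primary test to reject, which has probability at most 5%. If the devices truly differ, at most one device can equal no mouthguard, and Holm covers it. Simulated with Wilcoxon under equal means, familywise error is 4.7%. If a failed primary test is followed by Holm on all three pairs, it rises to 7.0%.

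**The case against.** A reader might infer that the fallback is unadjusted by design and more than doubles the 5% error rate. The documents do not support that, for four reasons.

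- Unadjusted is an inference from silence. The text leaves the adjustment open.
- The fallback is presented as the counterpart of ANOVA with post hoc tests, and post hoc ordinarily means after a significant omnibus test. With exactly three conditions that gate is enough, and familywise error is about 4%. The 12% needs the gate to be absent. For the whole procedure, under the assumed Shapiro-Wilk rule, it also needs clearly non-normal data.
- The hypothesis concerns one pair, and a single 5% Wilcoxon test of it is valid. Tukey at 0.019 is simply more conservative.
- The 15% switching rate rests on a normality rule that the plan does not contain.

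All four stand, and they rule out a claim of lost error control. They leave the inconsistency untouched: two valid but different thresholds for the same question, with an unwritten judgement made after the data are seen deciding which applies. The Friedman gate does not remove it, as step 4 shows.

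**Conclusion.** The point holds as an inconsistency and a gap in pre-specification. The level for custom versus boil-and-bite is about 0.019 in one branch and 0.05 in the other, if no adjustment is applied there. The matching false-positive rates are about 2% and 5% when both devices differ equally from none. Each rate is acceptable by itself; leaving the choice between them to an undefined judgement is not.

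The 0.019 rests on the standard Tukey procedure with a pooled error term and three conditions. The power figures rest on assumed means and are illustrative. The sample size of 28, or 32 with drop-out, is not affected. Changing the plan is a cheap improvement that also raises power for the main comparison in the parametric branch, from about 39% to about 53% in the assumed case.

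**What to change.** Rewrite the Data analysis paragraph to say:

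1. Custom-fitted versus boil-and-bite is the single primary comparison, at two-sided 5% in both branches: a paired t test or, in the fallback, the Wilcoxon signed-rank test.
2. Only if it is significant are the two device-versus-none comparisons tested, with Holm. A failed primary test is not followed by a further Holm round over all three pairs, which would raise familywise error to about 7%.
3. Normality is judged on the paired differences, by a method and cut-off written down before analysis.

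The switch then selects a test but no longer changes the significance level.

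The cost is a few sentences, with no new data and no change in numbers. The device-versus-none comparisons become secondary and conditional on the primary result. Because 28 was derived for the three-condition F test, the sample size paragraph should add a sentence on power for the primary pair.
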